NCT03966573

Title: «Evaluation of physical function, Quality of Life and Hip- and Knee Osteoarthritis Minimum 15 years After femoral Lengthening».

Date: 01.06.2018

Introduction

Limb lengthening is an established method for treatment of leg length discrepancy (anisomelia) or short stature (Castelein & Docquier, 2016; Steen, Terjesen, & Bjerkreim, 1997). The most common cause of limb lengthening is anisomelia (Castelein & Docquier, 2016). Anisomelia can either be innate or acquired, for instance after an injury (Castelein & Docquier, 2016). At Oslo University Hospital, it is performed 15-20 lower extremity lengthening procedures yearly including tibial and femoral lengthening. The vast majority of these are performed on patients with congenital deformities or other skeletal pathologies, and only a few are without a clear diagnosis or with acquired leg length discrepancy. Leg length discrepancy can be problematic as it often causes pelvic tilt towards the short side (Steen et al., 1997). This again, can cause functional scoliosis, largely affecting the gait (Steen et al., 1997). It is documented that anisomelia of more than two cm should be treated (Steen et al., 1997). Treatment could be either conservative by using shoe lift or surgical, where the long leg could be shortened or the short leg lengthened (Steen et al., 1997). In growing children there's also the possibility to stop growth in the long leg at a certain time to achieve leg length equality (isomelia) (Steen et al., 1997). In many patients, limb lengthening will of various reasons be preferred, if the discrepancy is over three cm (Steen et al., 1997).

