There is of considerable value to both patients and treating health professionals to be aware of what long term consequences to expect after limb lengthening when operative or conservative strategy of treatment is to be decided. Based on this, we want to evaluate physical function, quality of life and development of hip- and knee osteoarthritis minimum 15 years after femoral lengthening due to idiopathic or acquired leg length discrepancy.

Responsibility and sponsorship

Oslo University Hospital is responsible for the study, and Sophies Minde AS has sponsored the project by granting a research scholarship paying the salary for the researcher to be able to implement this study. All data will be collected at Oslo University Hospital. Radiologic examinations will be performed by radiographic section at Oslo University Hospital, while all other data will be collected by the researcher.

Purpose of the study and research questions

The purpose of this study is to evaluate physical function (range of motion, 30 seconds sit to stand test, stair test and hop tests), quality of life, health status, activity level and development of osteoarthritis in the hip- and knee joint minimum 15 years after femoral lengthening due to idiopathic or acquired leg length discrepancy.

Research questions:

- 1. Are there differences in physical function in the lower extremities in patients who have undergone femoral lengthening compared to reference values?
- 2. Do patients who have undergone femoral lengthening achieve recommendations for physical activity?
- 3. Are there differences in quality of life in patients who have undergone femoral lengthening compared to reference values?
- 4. Are there differences in health status in patients who have undergone femoral lengthening compared to reference values?
- 5. Are there differences in development of osteoarthritis in lengthened and unlengthened hip- and knee joint in patients who have undergone femoral lengthening?

Design, material and method

This study is a quantitative cross-sectional study.

Patients

Includable patients for this study will be identified from protocols from the surgical department.

Inclusion criteria: Patients with idiopathic (unknown cause) or post traumatic leg length discrepancy, that has been operated with femoral lengthening with callotasis minimum 15 years ago.

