Knee Osteoarthritis Outcome Score (KOOS) is a self-administered questionnaire. It has shown validity and reliability measuring function and pain in patients with knee injuries and osteoarthritis (Roos & Lohmander, 2003; Roos, Roos, Lohmander, Ekdahl, & Beynnon, 1998). The participant answer questions regarding pain, function, stiffness and quality of life regarding knee pain.

EQ-5D-5L has shown validity and reliability measuring health related quality of life in patients with hip- and knee pain (Fransen & Edmonds, 1999). It is a self-administered questionnaire where the participants report the extent of problems they have in the five dimensions mobility, self-care, usual activities, pain/discomfort and anxiety/depression. The questionnaire also contains a vertical analogue scale with the labelled endpoints 0-100 giving a valuation of the participants own health state that can be used as a quantitative measure of health outcome based on the patients' own judgement. The use of this questionnaire is approved by EuroQol.

International Physical Activity Questionnaire (IPAQ) short version has shown validity and reliability, and is a self-administered questionnaire used to obtain estimates of physical activity level (Cerin et al., 2016). Participants answer the amount of time being in vigorous activity, moderate activity, walking and sitting during the last 7 days. This will be transitioned into MET-score.

Radiology

Osteoarthritis in hip- and knee joints will be evaluated by measuring joint space width (JSW) and Kellgren & Lawrence classification (KL) (Terjesen & Gunderson, 2012). Leg length equality will be evaluated with standing axis measurements. All radiologic measurements are done by an experienced radiologist at Oslo University Hospital. Lengthened side will be compared to unlengthened side.

Analyzes

AROM in the hip and knee joint: The lengthened and unlengthened side will be compared using to-sample t-test.

30Ssts: We will analyze if there is a difference between patients that have undergone femoral lengthening and reference values with Wilcoxon signed ranks test (Tveter et al., 2014).

Stair test: We will analyze if there is a difference between patients that have undergone femoral lengthening and reference values with Wilcoxon signed ranks test.

Hop tests: The results will be analyzed comparing lengthened and unlengthened side using Wilcoxon signed ranks test.

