KOOS: To analyze if there is a difference between patients that have undergone femoral lengthening and reference values, one-sample t-test will be used.

EQ-5D-5L: We will analyze if there is a difference between patients that have undergone femoral lengthening and reference values with one-sample t-test

IPAQ: To analyze if the patients meet recommendations for physical activity of 600 MET, one-sample t-test will be used (ASCM, 2013).

JSW and KL: Evaluation of osteoarthritis development in the lengthened and unlengthened side will be presented by descriptive statistics.

Research ethics assessment

Possible negative consequences of this project are that the participants will have to use their time without being economically compensated, and they will be exposed to x-rays that are not medically induced. On the other hand, the participants are offered a thorough examination of their hips and knees, both clinically and radiological, in addition to participate in research that may be beneficial for other patients going through the same procedure.

Usefulness

The aim of the study is to increase knowledge about function, quality of life and risk of developing osteoarthritis after femoral lengthening. it is of importance for both patients and clinicians to be aware of possible long-term consequences of the treatment. All patients that

are treated with femoral lengthening at Oslo University Hospital nowadays, are close monitored by physiotherapist first in hospital care, and then locally after discharge. As there is lack of available research on the field, our results can be of interest for both patients, orthopedists, physiotherapists and other health care professionals.

Approvals and registrations

- Regional ethics committee: 2018/416 REK South East B.
- Data protection officer at Oslo University Hospital: 18/08589.
- Radiographic section at Oslo University Hospital: 1829.
- ClinicalTrials.gov: NCT03966573.

Reference list

- American College of Sports Medicine. (2013). ACSM's health-related physical fitness assessment manual: Lippincott Williams & Wilkins.

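### The only IPAQ analysis tests the group mean against 600 MET, so it does not show how many patients reach the physical-activity recommendation that research question 2 asks about

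*Combined protocol and SAP*

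**What the plan says.** Under Purpose of the study and research questions, question 2 asks: "Do patients who have undergone femoral lengthening achieve recommendations for physical activity". Questions 1, 3 and 4 are worded as comparisons with reference values; question 3, for example, asks "Are there differences in quality of life in patients who have undergone femoral lengthening compared to reference values".

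Under Questionnaires, the IPAQ short form is described: "Participants answer the amount of time being in vigorous activity, moderate activity, walking and sitting during the last 7 days". The next sentence adds "This will be transitioned into MET-score". So each participant has a score from a 7-day recall, but no variable is defined for having met or not met the recommendation.

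Under Analyzes, the one entry for IPAQ is "To analyze if the patients meet recommendations for physical activity of 600 MET, one-sample t-test will be used". No unit or period is attached to the 600. In that section descriptive reporting is named only for the radiographic outcomes: "Evaluation of osteoarthritis development in the lengthened and unlengthened side will be presented by descriptive statistics".

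**The concern.** A recommendation is met or missed by a person. The natural answer to question 2 is therefore the share of patients who reach the threshold, and the wording of the IPAQ analysis line itself is about patients meeting it. A one-sample t-test answers something else: whether the population mean differs from 600.

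The two can diverge. A MET total cannot be negative and is probably right-skewed (an assumption; the protocol gives no distribution). A few very active patients can then pull the mean well above 600 while half of the group stays below it. A significant result could be reported as patients meeting the recommendation, and no figure in the planned output would show otherwise.

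A smaller point is that the 600 MET threshold has no stated unit or period, so the plan does not say that it is on the same scale as the 7-day total.

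**Working it through.** **Inputs.** From the protocol: the threshold of 600, the one-sample t-test, and a score per patient. The protocol states no sample size, significance level, standard deviation or expected proportion, so there is no planned figure to reproduce. The Introduction gives only current yearly volume, and says of the lengthening procedures that "only a few are without a clear diagnosis or with acquired leg length discrepancy". Assumed here: n = 10 to 40, two-sided 5% level, and the distributions below.

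**Step 1: the mean does not fix the share.** Take a log-normal score with mean M and coefficient of variation c. Then σ = √ln(1 + c²), μ = ln M − σ²/2, and the share at or above 600 is 1 − Φ((ln 600 − μ)/σ). For M = 1000 and c = 1: σ = 0.833, μ = 6.561, ln 600 = 6.397, z = −0.197, share 58%.

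| Mean | c = 0.5 | c = 1.0 | c = 1.5 |
|---|---|---|---|
| 600 | 41% | 34% | 29% |
| 1000 | 80% | 58% | 47% |
| 1500 | 96% | 75% | 62% |

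**Step 2: the same test conclusion fits very different shares.** With t = (mean − 600)/(SD/√n) and n = 20:

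- 12 patients at 400 and 8 at 3000: mean 1440, SD 1307, t = 840/292 = 2.87, p = 0.010; 8/20 (40%) reach 600.
- 10 at 300 and 10 at 3000: mean 1650, SD 1385, t = 1050/310 = 3.39, p = 0.003; 10/20 (50%) reach it.
- Four each at 650, 700, 750, 800 and 850: mean 750, SD 72.5, t = 150/16.2 = 9.25, p < 0.001; 20/20 (100%) reach it.

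**Step 3: a less artificial sample.** Of 20 patients, 11 are evenly spaced over 100–550 and 9 over 1500–4500. The mean is (11 × 325 + 9 × 3000)/20 = 1528.75 and the SD is 1523, so t = 928.75/340.6 = 2.73, p = 0.013. The patient-level summary is 9/20 (45%; exact 95% CI 23–68%) with median 528 (IQR 314–2719). This shows what is possible, not what is typical.

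**Step 4: how often.** 100,000 samples per cell were simulated from log-normal (log-SD 0.8, 1.0, 1.2) and gamma (shape 1, 1.5, 2) models, scaled so that the true share below 600 was 50% or 60%. Ranges are over the six models. Significant means p < 0.05 with the mean above 600.

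| n | Significant, 50% below | Significant and at most half of the sample at or above 600, 50% below | Significant, 60% below |
|---|---|---|---|
| 10 | 4–5% | under 0.05% | 0.7–1% |
| 20 | 10–20% | 0.1–2% | 0.8–4% |
| 30 | 17–41% | 0.7–11% | 0.8–8% |
| 40 | 24–60% | 2–23% | 0.9–14% |

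With 50% below, the true mean in these models is 715 to 1233, so rejection is correct as a statement about the mean.

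**Step 5: precision of the proposed estimate.** Exact (Clopper-Pearson) 95% intervals when half reach 600: 5/10, 19–81%; 10/20, 27–73%; 15/30, 31–69%; 20/40, 34–66%.

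**The case against.** The strongest reply is that the protocol defines question 2 itself, at group level. It assigns a one-sample t-test against a fixed value, as it does for KOOS and EQ-5D-5L, and never defines a patient-level indicator. On that reading the test answers the question, and the wording contrast with the other questions only reflects that the comparator is a recommendation rather than a population norm. This stands in part: the group-mean reading is possible and the test is valid for it. But it does not tell a patient or clinician how many reach the recommended level.

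Next, the size is wholly assumed. If nearly all patients exceed 600, the mean and the share point the same way. If the sample is small, as the Introduction's account of current volume may suggest, the openly misleading sample is rare: under 0.05% at n=10 and about 0.1–2% at n=20, even with half truly below. That is correct and limits the weight of the point. The gap itself does not depend on that case, because the share is missing from the planned output whatever the p-value.

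A third reply is that one-line analysis entries do not exclude routine descriptive reporting. That is true, but naming the figure in advance avoids choosing it after the results are seen.

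Finally, a proportion loses efficiency, has a wide interval in a small sample, and comes with no stated share that would count as success. All three are fair. They are reasons to keep the mean comparison beside the proportion, not to leave the proportion out.

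**Conclusion.** The concern holds, as a minor one. The t-test is a valid test of the mean, but the mean does not determine the share of patients reaching 600, and no planned IPAQ figure shows that share. That the analysis is absent is certain from the text. The practical size is not known: the simulated frequencies rest on assumed skewed distributions, on n between 10 and 40, and on a true share below 600 of 50% or 60%, none of which the protocol supplies. One of five research questions is affected. The missing unit and period for the threshold would, by itself, be no more than a missing detail.

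**What to change.** In the IPAQ entry under Analyzes:

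- Make the main analysis for question 2 the number and percentage of patients with a MET total at or above 600, with an exact (Clopper-Pearson) 95% confidence interval.
- Describe the MET total by median and interquartile range.
- Keep the one-sample comparison of the mean with 600 as secondary, and state that it will not be read as showing that patients meet the recommendation.
- State the unit and period of the 600 MET threshold so that it matches the 7-day IPAQ total.

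The cost is one or two lines of text. The individual scores are collected anyway, so no new data, visits or patients are needed. The price is lower efficiency than an analysis of the mean and a wide interval in a small sample.

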
Textbooks describing limb lengthening claims that it increases the risk of osteoarthritis (Sneppen, Bünger, Hvid, & Søballe, 2014), but to our knowledge this statement lacks research evidence and appears more like an assumption. Animal research have shown tendencies of knee osteoarthritis after femoral lengthening (Stanitski, 1994), but we have only succeeded in finding one article that describes osteoarthritis development after femoral lengthening on humans, where 18 out of 23 patients showed knee osteoarthritis with a mean follow-up of 6 years after femoral and / or tibial lengthening (Jeong, Inan, Riddle, Gabos, & Bowen, 2006).

It is an interesting finding, but this study used another lengthening method than today's gold standard of callotasis and were performed on patients with congenital femoral deficiency. It is hard to say if the osteoarthritis seen in these patients is in context with the lengthening procedure with their method of choice or the patient's pathology. It is important to know if the procedure itself increases the risk of developing osteoarthritis. In our study we will therefore only include patients with idiopathic or acquired leg length discrepancy, minimizing as far as we can the risk of the patient's pathology being the explanatory factor for eventual findings. Socioeconomically it's relevant to know whether limb lengthening increases the risk of osteoarthritis, as the condition leads to pain and reduced function, and can cause considerable costs regarding sick leaves, medications, physiotherapy and possibly prosthetic operations (Bitton, 2009; Grotle, Hagen, Natvig, Dahl, & Kvien, 2008). It can take time from an initial factor until osteoarthritis can be confirmed by conventional radiology, and all the research we have been able to find describing consequences of limb lengthening, all have relatively short follow-up, mostly far below ten years. With the lack of research available in the question of context between limb lengthening and risk of osteoarthritis, there is an obvious need for more research to investigate this with long enough follow-up to be able to identify osteoarthritis within the patient group.

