Exclusion criteria: Innate skeletal pathology leading to shortening of the lower extremity, malangulation and less developed musculature, such as congenital femoral deficiency (CFD) or fibular hemimelia (Jeong et al., 2006). Patients with acquired leg length discrepancy after

infection in hip- or knee joint, and patients that have inserted hip- or knee prosthesis will also be excluded.

Data collection

All examinations will be completed at the same day at Oslo University Hospital.

Outcome measures

Physical function

Active range of motion (AROM) of the hip- and knee joint will be measured in degrees with an analog goniometer. Even though goniometric measures have uncertainties, acceptable intra-tester reliability is shown in hip and knee measurements with analog goniometer (Holm et al., 2000; Watkins, Riddle, Lamb, & Personius, 1991).

30 seconds sit to stand test (30sSTS) measures lower extremity strength (Bennell, Dobson, & Hinman, 2011; Csuka & McCarty, 1985). Chair with height of 44-45 cm will be used. The participant is told to sit and stand as many times as possible within 30 seconds, and the total number is registered (Tveter, Dagfinrud, Moseng, & Holm, 2014).

Stair test measures submaximal cardiopulmonary endurance (Cataneo & Cataneo, 2007). The participant is asked to move as fast as possible 18 stairs $(17\pm1 \text{ cm})$ up and down three consecutive times. Total time in seconds is registered. The participant is allowed to run and use the banister if needed. The participant has to step on every stair. Pulse is measured, and Borg scale 6-20 registered immediately after the test (Tveter et al., 2014).

Hop tests will be used to compare function in the lengthened and unlengthened limb. The tests are developed for patients with ACL ruptures, but the high specificity and low false positive rates found is an argument for us to use it to separate the limbs from each other and confirm if there is impaired lower limb function (Noyes, Barber, & Mangine, 1991). Single hop for distance, triple hop for distance, timed hop (seconds used to hop 6 m) and cross-over hop for distance (triple cross-over hop over 15 cm wide tape) will be performed on both legs.

Questionnaires

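### Research question 5 compares osteoarthritis between lengthened and unlengthened joints, but only descriptive statistics are planned for JSW and KL

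*Combined protocol and SAP*

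**What the plan says.** Question 5, under Purpose of the study and research questions, is comparative: "Are there differences in development of osteoarthritis in lengthened and unlengthened hip- and knee joint in patients who have undergone femoral lengthening". The Radiology section names JSW and KL as the measures for hip and knee and adds: "Lengthened side will be compared to unlengthened side". The Introduction explains why this matters: "It is important to know if the procedure itself increases the risk of developing osteoarthritis".

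The Analyzes entry for JSW and KL reads in full: "Evaluation of osteoarthritis development in the lengthened and unlengthened side will be presented by descriptive statistics". The two other side-to-side outcomes in that section each have a named test. For active range of motion (AROM): "The lengthened and unlengthened side will be compared using to-sample t-test". For the hop tests: "The results will be analyzed comparing lengthened and unlengthened side using Wilcoxon signed ranks test".

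Two further statements limit what any side comparison can mean. Under Design, material and method: "This study is a quantitative cross-sectional study". Under the exclusion criteria: "patients that have inserted hip- or knee prosthesis will also be excluded".

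**The concern.** The question and its analysis do not match. A descriptive table can show that one side looks worse, but not how far the difference could be due to chance. If only per-side summaries are printed, the pairing within patients is lost too, and a reader cannot recover the uncertainty from the table.

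Osteoarthritis is in the study title, and the Introduction says human evidence on it is scarce. The Usefulness section says patients and clinicians need to know the possible long-term consequences. Reading a chance imbalance as harm, or a small observed difference as reassurance, would mislead both groups. Leaving the contrast and the KL cut-off open also allows them to be chosen after the data have been seen.

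**Working it through.** **Reading the plan.** There is no stated figure to reproduce: the documents give no sample size, SD, osteoarthritis rate, alpha or power. The Analyzes section has eight entries. Seven name a test (AROM, 30-second sit to stand, stair test, hop tests, KOOS, EQ-5D-5L, IPAQ). Only the JSW and KL entry, which is the one that answers question 5, does not. No other section supplies an interval or test for these measures.

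**Illustration.** Every n, count and SD below is an assumption. Let b be the number of patients affected on the lengthened side only, and c the number affected on the unlengthened side only. The paired risk difference is (b − c)/n. Its Tango score 95% limits are the values Δ that solve

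(b − c − nΔ) / √{n[2q + Δ(1 − Δ)]} = ±1.96,

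where q = [√(B² − 4AC) − B]/(2A), A = 2n, B = −b − c + (2n − b + c)Δ and C = −cΔ(1 − Δ).

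*1. KL present or absent, observed difference zero.* With b = c = 2:

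| n | Difference | 95% CI, percentage points |
|---|---|---|
| 10 | 0 | ±40 |
| 20 | 0 | ±23 |
| 30 | 0 | ±16 |

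Check at n = 20, Δ = 0.230: A = 40, B = 5.2, C = −0.354, so q = 0.049. The ratio is −4.60/√5.52 = −1.96.

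Fixing b = c = 2 lets the discordant share fall from 4/10 to 4/30 as n grows. Holding it at 20% instead (b = c = 1, 2, 3 at n = 10, 20, 30) gives ±34, ±23 and ±18 points. The message is the same.

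*2. Same per-side table, different pairing.* Take 8/30 affected on the lengthened side and 2/30 on the other, a difference of 6/30 = 20 points. The exact McNemar p is the two-sided binomial probability on b + c pairs with probability 0.5.

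| Affected on both sides | b | c | 95% CI, points | Exact McNemar p |
|---|---|---|---|---|
| 2 | 6 | 0 | 6 to 37 | 2 × 0.5⁶ = 0.031 |
| 0 | 8 | 2 | −1 to 40 | 2 × (45 + 10 + 1)/1024 = 0.109 |

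The margins fix the point estimate but not the uncertainty.

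*3. JSW.* Half-width = t(0.975, n − 1) × SD/√n, where SD is that of the within-patient difference.

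| n | t | SD 0.6 mm | SD 0.8 mm | SD 1.0 mm |
|---|---|---|---|---|
| 10 | 2.262 | 0.43 | 0.57 | 0.72 |
| 20 | 2.093 | 0.28 | 0.37 | 0.47 |
| 30 | 2.045 | 0.22 | 0.30 | 0.37 |

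**The case against.** Naming tests for seven outcomes and description for one looks deliberate, and descriptive reporting can be defended in a small single-centre cross-sectional study. Nor does it exclude a paired difference or a cross-tabulation of KL by side. The documents never say that a small difference will be reported as no added risk, and all the figures above rest on assumed inputs.

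There is also a causal objection. Post-traumatic cases are eligible, and in them the lengthened limb may also be the injured one, so the other limb is not a clean control. An interval covers sampling error only, and a p-value could lend authority to a confounded contrast.

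Part of this stands. The harm is a risk and not a certainty, the figures show only how wide the intervals could be, and the post-traumatic caveat belongs in the report. The AROM entry is a weak model as well, since it does not clearly say the test is paired. None of it removes the mismatch. The plan gives no reason for treating this outcome differently and does not say what the description will contain. A small cohort makes an interval more necessary, not less.

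**Conclusion.** The concern holds. The plan poses a comparative question about osteoarthritis and announces a side-to-side comparison, but prespecifies no estimate of the difference and no measure of its precision. That the omission is real rests on the text alone, with high confidence. How much it matters depends on the unstated sample size and variability: under the assumptions shown, an observed KL difference of zero at 10 to 30 patients is compatible with a true difference of roughly 16 to 40 percentage points in either direction. The data to be collected are unaffected, so this should be corrected but does not invalidate the study.

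**What to change.** In the JSW and KL entry of the Analyzes section, add for hip and knee separately:

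- the mean within-patient JSW difference (lengthened minus unlengthened) with 95% CI;
- one paired KL comparison: the paired risk difference with 95% CI and exact McNemar test at a KL cut-off stated in advance. A Wilcoxon signed ranks test on KL grade is an acceptable alternative.

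State that these four comparisons (two measures, two joints) are not adjusted for multiplicity. Keep the descriptive tables and include the paired KL cross-tabulation. Draw the conclusion from the intervals, so that a non-significant result is not reported as no increased risk.

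State also that the result is a side difference at follow-up among patients without a hip or knee prosthesis. The design is cross-sectional, no baseline radiographs are mentioned, and in post-traumatic cases the injury may have affected the same limb. The result should therefore not be presented as the effect of lengthening alone.

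If the analysis is to stay descriptive, reword question 5 as descriptive and draw no conclusion on risk.

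The cost is a few lines of text and minutes of analysis on data already planned. The intervals may be wide if the sample is small, and that should be shown rather than left out.
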